5.3.5 Corticosteroids

Participants may receive topical or inhaled corticosteroids while on study. The use of systemic corticosteroids is discouraged except as needed for prevention or treatment of infusion reactions related to ofatumumab, or as needed for therapy of transaminitis. However, participants who develop severe or life-threatening conditions that may be alleviated by systemic corticosteroid therapy are permitted to receive such drugs and are not required to discontinue study participation.

5.3.6 Prophylactic Antibiotics

Because of the observation of two cases of PCP in this study, PCP prophylaxis is required for all participants initiating therapy on study. At the same time antiviral prophylaxis against HSV and VZV is also required, because of the frequency of reactivation of these viruses in CLL participants.

5.3.7 Immunization

Because of its actions to inhibit PI3K δ -dependent B-cell function, high doses of idelalisib can impair primary or secondary responses to immunization in animals. The specific clinical relevance of these nonclinical findings is unknown. However, for participants who are at substantial risk of an infection (eg, influenza) that may be prevented by immunization, consideration should be given to providing the vaccine prior to initiation of treatment with idelalisib if at all possible, and if not, then vaccination should be provided during idelalisib therapy.

5.4 Duration of Therapy

The planned duration of induction therapy is 8 months of induction therapy. For those still in the midst of induction, they may complete the planned 6 months of ofatumumab therapy followed by

CONFIDENTIAL

This document is confidential. Do not disclose or use except as authorized.

observation. Protocol follow-up may continue until achievement of CR, or indefinitely, until one of the following criteria applies:

- Disease progression,
- Intercurrent illness that prevents further administration of treatment,
- Unacceptable adverse event(s),
- Participant demonstrates an inability or unwillingness to comply with the oral medication regimen and/or documentation requirements
- Participant decides to withdraw from the study, or
- General or specific changes in the participant's condition render the participant unacceptable for further treatment in the opinion of the treating investigator.

5.5 Duration of Follow Up

Once participants have completed study treatment they will be followed until initiation of new therapy following removal from study, or until death, whichever occurs first. They will be seen every 3 or 6 months in the follow up phase; this will be decided by their treating physician. Follow up will continue for up to 10 years. Participants removed from study for unacceptable adverse events will be followed until resolution or stabilization of the adverse event, and/or until initiation of new therapy for their disease, whichever is longer.

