17. APPENDICES76

1. OBJECTIVES

1.1 Study Design

This study was designed to enroll 50 subjects with untreated chronic lymphocytic leukemia/small lymphocytic lymphoma (CLL/SLL) who meet IWCLL 2008 criteria for initiation of therapy will initiate single-agent idelalisib (GS1101), a PI3K delta specific inhibitor, daily for the first two months on study, and begin ofatumumab at the start of the 3rd month following a complete response evaluation. The duration of combination therapy will be 8 months. All subjects will receive 8 weekly doses of ofatumumab, following which they will undergo another response evaluation. They will then continue with idelalisib during their 4 monthly doses of ofatumumab. The final primary endpoint response evaluation will occur two months after completion of ofatumumab, at 10 months following start of therapy. Therapy with idelalisib will continue throughout the ofatumumab therapy and after, until development of progressive disease. Once participants are receiving single agent idelalisib therapy they will be seen in clinic every 2 months. After treatment is complete subjects will be followed every 3-6 months at the treating investigator's discretion until initiation of a new therapy or death. Subjects who do not complete cycle 2 are not considered evaluable for the study efficacy objectives and may be replaced. Their data will be included in all toxicity evaluations.

As of 3/11/2016, Gilead has observed an excess of infectious deaths in three trials, one in upfront CLL, and as a result the FDA and Gilead are discontinuing enrollment to upfront CLL trials as well as discontinuing the administration of idelalisib to patients previously enrolled on these trials. All patients on this trial however may receive ofatumumab as planned and continue to be followed per protocol. Correlative analyses will continue as previously planned.

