This study activated for enrollment on June 16, 2014, and since then 15 patients have initiated on therapy. Among the first 8 patients to reach cycle 2, two patients developed grade 4 transaminitis. Transaminitis is a well-known side effect of idelalisib, and included as a black box warning in the FDA approved label. In these two cases the onset was rapid, and continued to increase after discontinuation of the drug. We have therefore previously amended the protocol to significantly increase the frequency of LFT monitoring during the high risk period. Additional observation has shown that this transaminitis appears to be inflammatory, based on the results of two liver biopsies showing a CD8 T cell infiltrate and the response of these patients to steroids and/or mycophenolate mofetil. We have developed an algorithm for the early initiation of steroids with the first signs of transaminitis which together with the frequent monitoring has resulted in predictable safety and much shorter drug interruptions. This amendment served to further refine that treatment algorithm.

An amendment was submitted in January 2015 to add correlative studies, in particular sequencing analysis of the clonal composition of CLL in PB vs BM at baseline, mid treatment and at final restaging. This analysis will still occur.

Rationale for Current Amendment 3/14/16

This amendment will take all patients off idelalisib, but allow them to receive ofatumumab and be followed per protocol assessments. All patients had discontinued idelalisib as of 3/11/16. They will undergo a full disease restaging with correlative samples within 30 days and be followed per protocol until further therapy, and after that just for overall survival.

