Banking at Clinical Research Consortium for Sites not participating in a CRC study ¹⁸	X		C 3 D1						X	
PK samples, ofatumumab ⁵			C3 D1, 8, 15; C4 D 22	CYCLE 5 D 1 & CYCLE 8 D 1		FINAL ONLY		6 MOS		
PK samples, idelalisib ⁵		DAY 1 EACH CYCLE	CYCLE 3 DAY 1, CYCLE 4 DAY 22	CYCLE 8 DAY 1		FINAL ONLY		6 MOS		
OSU Studies ⁶	X	CYCLE 1 DAY 1, 15; CYCLE 2 DAY 1	CYCLE 3 DAY 1			TWO MONTH ONLY				
Mayo Studies ⁷	X		CYCLE 3 DAY 1			FINAL ONLY			EVERY 6 MONTHS FOR FIRST YEAR; & AT PD	
Physical Exam	X	WEEKLY	CYCLE 3 DAY 1, 8, 15, CYCLE 4 DAY 1, 15	MONTHLY	X	X	X	X	X	
ECOG	X	WEEKLY	WITH PE	WITH PE	X	X	X	X		
Height	X						X			
Weight	X		X	X	X	X	X	X		
Vital Signs ¹²	X	WEEKLY	WEEKLY	MONTHLY	X	X	X	X	X	
12-lead ECG	X									
Procedures	Screen	Treatment Phase					Post Induction Phase		Long Term Follow-up	Survival Follow-up
		Cycle 1-2 Idelalisib only (Days 1-56)	Cycle 3 & 4 Weekly Ofa + Idelalisib ¹⁵	Cycle 5-8 Monthly Ofa + Idelalisib	Restage Cycle 4 day 22	Cycle 2 day 22 (Restage end of cycle 2), Cycle 10 day 1 (Final Restage 2 months after end of ofa therapy) and off treatment prior to cycle 10	Cycle 9 Day 1	Every 2 mos while on study drug beginning Cycle 10	Every 3 or 6 months ¹¹	Yearly

CONFIDENTIAL

This document is confidential. Do not disclose or use except as authorized.

Adverse Events	X	WEEKLY	WITH PE	WITH PE	X	X	X	X	X ⁸	
Concomitant Therapy	X	WEEKLY	WITH PE	WITH PE	X	X	X	X		
Chemistry ¹³	X	WEEKLY ¹³	WEEKLY THROUGH H C4 D 22 ¹³	MONTHLY	X	X	X	X	X	
Hematology ¹⁴	X	WEEKLY	WEEKLY THROUGH H C4 D 22	MONTHLY	X	X	X	X	X	
Beta-2-microglobulin	X				X	X		EVERY 6 MOS	EVERY 6 MOS	
Immunoglobulins (IgG, IgM, IgA)	X				X	X		EVERY 6 MOS	EVERY 6 MOS	
Serum protein electrophoresis	X				X	X		EVERY 6 MOS	EVERY 6 MOS	
CD4 count	X				X	X		EVERY 6 MOS	EVERY 6 MOS	
Direct Coombs test	X									
Serum Pregnancy Test ⁹	X		MONTHLY	X		X		ONCE 5 MONTHS POST OFA		
Hepatitis B surface antigen and antibody ¹⁰ , Hepatitis C antibody, HIV	X									
Survival follow-up by telephone or clinic visit note										X

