10.1.7 Time to progression, progression-free survival, and overall survival

Time to progression (TTP) is defined as the time from study entry until objective disease progression (see above). Progression-free survival (PFS) is defined as the time from study entry until objective disease progression or death. Overall survival is defined as the time from study entry until death from any cause, and is measured in the intent-to-treat population.

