14.2 Analysis of Secondary Endpoints

Other Secondary Objectives:

- To determine the CR rate and PFS of ofatumumab and idelalisib.
- To determine the ORR, CR and rate of nodal PR with lymphocytosis for idelalisib given alone for 2 months.
- To assess the safety of ofatumumab and idelalisib in combination.
- To determine whether clinical response correlates with known CLL molecular prognostic factors.
- To determine whether the use of CT scans in response assessment improves the predictive power of ORR for progression-free or overall survival.
- To determine whether serum ofatumumab levels in vivo predict response.
- To assess whether idelalisib alters the flow cytometric phenotype of circulating CLL cells.
- To assess whether in vivo treatment with idelalisib alters CLL cell sensitivity to therapy with antibodies or other kinase inhibitors
- To assess pharmacodynamic markers of PI3 kinase inhibition including AKT phosphorylation, production of T cell chemokines and response to CXCR 4/5
- To determine whether response or resistance correlates with genetic alterations in PIK3CA or PIK3CD or other genes
 - To assess the clonal dynamics of CLL in peripheral blood vs bone marrow, and during therapy with idelalisib.

Secondary Analysis:

The CR rate of combination therapy, ORR rate, and rate of nodal PR with lymphocytosis for idelalisib given alone for 2 months will be summarized as numbers and percentages. The Kaplan Meier method will be used to estimate the median progression free survival. The number and percent of patients who experience toxicities on combination therapy after at least one dose of treatment will also be summarized. Associations of clinical response rate and known prognostic factors will be assessed using Fisher's exact test.

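### Sections 1.1 and 5.5 end follow-up at new therapy while 2.5 and Table 10 continue it for survival, so deaths after a switch may not be collected

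*Combined protocol and SAP*

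**What the plan says.** The current text gives several rules for when follow-up ends.

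- **Section 1.1 (Study Design):** after treatment, follow-up every 3 to 6 months "until initiation of a new therapy or death".
- **Section 5.5 (Duration of Follow Up):** "they will be followed until initiation of new therapy following removal from study, or until death, whichever occurs first". The same paragraph adds: "Follow up will continue for up to 10 years". Patients removed for an unacceptable adverse event are followed to its resolution or stabilisation, and/or to new therapy, whichever is longer.
- **Section 2.5 (rationale for the amendment of 3/14/16):** patients will "be followed per protocol until further therapy, and after that just for overall survival".
- **Section 9, Table 10:** a Survival Follow-up column headed Yearly, separate from the Long Term Follow-up column (every 3 or 6 months), with the row "Survival follow-up by telephone or clinic visit note".
- **Table 10, footnote 11:** patients who stop for an adverse event with stable disease or better are followed to relapse or progression, new therapy, or 12 months, whichever is first.
- **Section 5.4 (Duration of Therapy):** protocol follow-up may run indefinitely until a listed criterion applies. The list includes progression and unacceptable adverse events.

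The endpoints that depend on these rules are in 10.1.7: "Overall survival is defined as the time from study entry until death from any cause, and is measured in the intent-to-treat population", and "Progression-free survival (PFS) is defined as the time from study entry until objective disease progression or death". Neither definition says what happens at new therapy. Section 14.2 estimates median PFS by Kaplan-Meier. It also asks whether CT-based response assessment "improves the predictive power of ORR for progression-free or overall survival".

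**The concern.** Section 5.5 is where a site looks to learn when a patient's follow-up is over. Read literally, it closes the patient at the start of the next therapy. The survival phase after that point is stated only in the amendment rationale in 2.5. Table 10 has the column but does not say what moves a patient into it.

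Two sites could therefore both comply with the protocol and hold different survival data, within a cohort of 27. At a site that stops at the switch, OS is in effect censored at next therapy. PFS is touched as well: if a patient starts new therapy without documented progression, a later death belongs in PFS under 10.1.7 but would not be collected under 5.5. Such switches are possible here because idelalisib, planned until progression, was stopped for all patients by 3/11/16 whatever their response.

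**Working it through.** The documents give no OS event count, rate or power, so there is no stated figure to reproduce. The check is a comparison of the rules, followed by an illustration of when the gap biases OS.

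**Step 1. One hypothetical patient under each rule.** Suppose a patient completes ofatumumab in year 1, starts another therapy in year 3 without documented progression, and dies in year 5.

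- *Sections 1.1 and 5.5:* follow-up ends in year 3. The death is not collected, and OS and PFS can only be censored at or before year 3.
- *Section 2.5 with Table 10:* yearly survival contact continues, so the death in year 5 is recorded. Progression between years 3 and 5 is not, because collection after further therapy is for survival only.
- *Footnote 11,* if this patient had stopped for an adverse event with stable disease or better: follow-up ends at 12 months, although 5.5 allows up to 10 years.
- *Safety reporting (11.8 and footnote 8):* deaths are reportable for six months after the last study intervention or completion of therapy. That window closed long before year 5.

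The rules therefore differ on whether this death enters the database.

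**Step 2. When the gap biases OS.** Let s be the yearly switch rate, h0 and h1 the death hazards before and after the switch, and T = 10 years (the limit in 5.5). **Every rate below is assumed; none is in the documents.**

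- Deaths before a switch, per patient: h0/(s+h0) × (1 − exp(−(s+h0)T)).
- Deaths after a switch, per patient: the integral from 0 to T of s·exp(−(s+h0)u)·(1 − exp(−h1(T−u))) du.
- True OS at T: 1 minus the sum of the two.
- Kaplan-Meier censored at the switch estimates exp(−h0·T).

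Example with s = 0.10, h0 = 0.02, h1 = 0.06:

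- Before: 0.02/0.12 × (1 − exp(−1.2)) = 0.1165; × 27 = 3.14 deaths.
- After: 0.10 × [(1 − exp(−1.2))/0.12 − exp(−0.6) × (1 − exp(−0.6))/0.06] = 0.10 × (5.823 − 4.127) = 0.1696; × 27 = 4.58 deaths.
- True OS: 1 − 0.1165 − 0.1696 = 0.71. Censored at the switch: exp(−0.2) = 0.82.

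| s | h0 | h1 | Deaths before switch | Deaths after switch | Share after | True 10-year OS | OS censored at switch |
|---|---|---|---|---|---|---|---|
| 0.10 | 0.02 | 0.02 | 3.14 | 1.75 | 36% | 0.82 | 0.82 |
| 0.10 | 0.02 | 0.06 | 3.14 | 4.58 | 59% | 0.71 | 0.82 |
| 0.20 | 0.02 | 0.06 | 2.18 | 7.04 | 76% | 0.66 | 0.82 |
| 0.30 | 0.03 | 0.10 | 2.36 | 11.98 | 84% | 0.47 | 0.74 |

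The first row matters most for interpretation. With equal hazards about a third of the deaths are lost, yet the Kaplan-Meier estimate is unbiased; only precision suffers. Bias appears when the hazard changes at the switch. The table takes the worst case, in which every site follows 5.5 alone, and subtracts nothing for deaths inside the six-month window.

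**The case against.** The best defence is that the intended design is clear. Section 2.5 states it, Table 10 separates long-term visits from yearly survival contact, and 12.1.2 schedules a Follow up/Survival Form tied to a visit or a call. The sentence in 5.5 about being seen every 3 or 6 months matches the Long Term column, so 5.5 can be read as covering clinic visits only. Footnote 11 is attached to that same column, and the list in 5.4 sits under a heading about therapy. All of this is fair, but none of these sections states the limitation. The stop in 5.5 is unqualified and shares a paragraph with the 10-year limit. Section 11.4.1 asks for deaths in long-term follow-up to be reported at continuing review, but a patient whose follow-up ended at the switch is no longer in that phase.

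Other parts of the defence stand and limit the point:

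- OS is not an objective in 1.2 or 1.3. The CT objective in 1.3 names PFS or time to next treatment; only the 14.2 version names OS, and 14.2 gives no OS method.
- Deaths within the six-month window are reported anyway.
- A reader might infer that 5.5 contradicts the OS definition. It does not: 10.1.7 sets the event and the population, not the length of follow-up. The stop weakens ascertainment.
- A reader might infer that 2.5 would rescue PFS. It would restore deaths, not later progressions.

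**Conclusion.** The inconsistency is real and sits in current text. Followed literally, 5.5 leaves uncollected any death that occurs after a switch and outside the six-month window. OS, and the deaths that count in PFS for patients who switch without progression, could be incompletely ascertained.

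The size is unknown. Each missed death is 1/27 = 3.7% of the cohort, but no document says how many patients will switch or die afterwards, or which rule sites apply. A reader might infer that OS is necessarily inflated, or take a row of the table as a forecast. Neither is supported: inflation requires a higher death hazard after the switch, which is plausible but undocumented, and the rows only span assumed rates. Nor do the excess deaths described in 2.2.4 show what happens here after a switch; they occurred in other trials and were mostly infectious. The primary ORR is unaffected. This is worth correcting, but it does not threaten the trial's main result.

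**What to change.** Reconcile 1.1, 5.4, 5.5 and footnote 11 with 2.5 and Table 10. Changing only 1.1 and 5.5 would leave two conflicting stops in place.

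1. State that disease follow-up visits end at new therapy, and that yearly survival status by telephone or clinic note then continues for all patients to death or the 10-year limit, unless consent is withdrawn. Say in Table 10 what moves a patient into the survival column.
2. State in 10.1.7 or 14.2 that OS is not censored at new therapy.
3. Record the date of new therapy and whether progression had been documented by then, so that the handling of new therapy in PFS can be stated in 14.2.

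The cost is amendment wording, two data items per switch and a few phone or chart checks a year. The ceiling is 27 contacts a year, reached only if all 27 patients had switched and were alive. The yearly contact and the Follow up/Survival Form already exist.

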5.6 Criteria for Removal from Study

Participants will be removed from study when any of the criteria listed in Section 5.4 applies. The reason for study removal and the date the participant was removed must be documented in the study-specific case report form (CRF). Alternative care options will be discussed with the participant.

In the event of unusual or life-threatening complications, participating investigators must immediately notify the Principal Investigator (or Protocol Chair) [name] at [contact] or pager at [contact] [name].

6. EXPECTED TOXICITIES AND DOSING DELAYS/DOSE MODIFICATIONS

Dose delays and modifications will be made using the following recommendations. Toxicity assessments for non-hematologic toxicity will be done using the CTEP Version 4.0 of the NCI Common Terminology Criteria for Adverse Events (CTCAE) which is identified and located on the CTEP website at:

http://ctep.cancer.gov/protocolDevelopment/electronic_applications/ctc.htm. Hematologic toxicity will be evaluated according to the IWCLL 2008 guidelines as outlined below and in Appendix C.

If possible, symptoms should be managed symptomatically. In the case of toxicity, appropriate medical treatment should be used (including anti-emetics, anti-diarrheals, etc.).

CONFIDENTIAL

This document is confidential. Do not disclose or use except as authorized.

All adverse events experienced by participants will be collected from the time of the first dose of study treatment, through the study and until the final study visit. Participants continuing to experience toxicity at the off study visit may be contacted for additional assessments until the toxicity has resolved or is deemed irreversible.

6.1 Anticipated Toxicities

A list of the adverse events and potential risks associated with the agents administered in this study appear below and will determine whether dose delays and modifications will be made or whether the event requires expedited reporting in addition to routine reporting.

Please note that if one study drug is held, the other will also be held. If drugs are held for more than half a week, then the assessment schedule will also be held until drug resumption.

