5. TREATMENT PLAN

Treatment will be administered on an outpatient basis. Expected toxicities and potential risks as well as dose modifications for ofatumumab are described in Section 6 (Expected Toxicities and Dosing Delays/Dose Modification). No investigational or commercial agents or therapies other than those described below may be administered with the intent to treat the participant's malignancy.

Idelalisib lead-in followed by ofatumumab 8 wks later

All therapy with idelalisib has been discontinued. Patients on drug stopped as of 3/11/16. Those currently receiving ofatumumab may complete the planned course and evaluations as below. Those who have not yet reached day 57 may initiate ofatumumab at present. On day 57, ofatumumab will begin with the 300 mg dose. Ofatumumab will then be administered at 1000 mg weekly to complete 8 weeks (days 64, 71, 78, 85, 92, 99, 106) throughout Cycles 3 and 4. Cycle 4 will last 49 days (7 weeks) to accommodate the Ofatumumab dosing schedule. This will be followed by monthly ofatumumab on weeks 20, 24, 28, 32 to complete 4 additional cycles (5-8). The overall induction treatment period will then be up to 8 months, including whatever idelalisib was received prior to March 11, 2016. Restaging with CT scans will happen after Cycle 2, on cycle 4 day 22, and a final restage will occur 2 months after the completion of ofatumumab. There will be a tumor response assessment done via physical exam after Cycle 8.

Table 1: Treatment Description

Agent	Pre-medications; Precautions	Dose	Route	Schedule	Cycle Length
Idelalisib	None	150 mg BID	Oral	Discontinued	28 days (4 weeks) (Except cycle 4-49 days, 7 weeks)
Ofatumumab	Pre-medication before each ofatumumab infusion must be given within 30 minutes to 2 hours prior to the treatment: Acetaminophen 1000 mg po Benadryl 50 mg IV or po Methylprednisolone 50 mg IV*	300 mg at 0.3 mg/ml in NS; followed one week later by 1000 mg at 1 mg/ml in NS	IV after administration of Idelalisib and premeds	Weekly x 8 doses, then monthly x 4 doses	
* If the 2 nd infusion has been completed without the subject experiencing any grade = 3 AEs, pre-medication with glucocorticoid may be reduced or omitted before the 3 rd to N th infusion at the discretion of the investigator.					

CONFIDENTIAL

This document is confidential. Do not disclose or use except as authorized.

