5.2 Agent Administration

5.2.1 Idelalisib will not be given

5.2.2 Ofatumumab

The dosing of ofatumumab in CLL should consist of an infusion of 300 mg on Day 1, an infusion of 1000 mg weekly for 7 additional doses, and then infusions of 1000 mg monthly for up to 4 doses. The monthly ofatumumab doses should be given on Day 1 of the cycles.

First Infusion of 300 mg Ofatumumab (CLL)

The first dose administered of ofatumumab in CLL should be 300 mg to minimize infusion reactions. The initial rate of the first infusion of 300 mg ofatumumab (0.3 mg/mL) should be 12 mL/h. If no infusion reactions occur the infusion rate should be increased every 30 minutes, to a maximum of 400 mL/h, according to Table 2. If this schedule is followed, the infusion duration will be approximately 4.6 hours. If the ofatumumab dose cannot be completed on day 1 in clinic, the remaining dose may be completed the following day with the same premedications.

Table 2: Infusion rate at 1st ofatumumab infusion (300 mg)

Time	mL/hour
0 – 30 minutes	12
31 – 60 minutes	25
61 – 90 minutes	50
91 – 120 minutes	100
121 - 150 minutes	200
151 - 180 minutes	300
181+ minutes	400

CONFIDENTIAL

This document is confidential. Do not disclose or use except as authorized.

If an infusion reaction develops, the infusion should be temporarily slowed or interrupted. Upon restart, the infusion rate should be half of the infusion rate at the time the infusion was paused. If, however, the infusion rate was 12 mL/hour before the pause, the infusion should be restarted at 12 mL/hour. Thereafter, the infusion rate may be increased according to the judgment of the investigator, in the manner described in this section. If the infusion is not completed on day 1, the remaining infusion may be completed on day 2 at the starting infusion rate used on day 1.

First Infusion of 1000 mg Ofatumumab

The initial rate of the first infusion of 1000 mg ofatumumab (1 mg/mL) should be 12 mL/h. If no infusion reactions occur the infusion rate should be increased every 30 minutes, to a maximum of 400 mL/h, according to Table 3. If this schedule is followed, the infusion duration will be approximately 4.6 hours. If the ofatumumab dose cannot be completed on day 1 in clinic, the remaining dose may be completed the following day with the same premedications.

Table 3: Infusion rate at 1st ofatumumab infusion (1000 mg)

Time	mL/hour
0 – 30 minutes	12
31 – 60 minutes	25
61 – 90 minutes	50
91 – 120 minutes	100
121 - 150 minutes	200

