Either or both drugs may be held for up to six weeks for resolution of toxicity without removing a participant from the study. Longer holds are acceptable in the post-induction phase following discussion with the overall principal investigator.

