7. DRUG FORMULATION AND ADMINISTRATION

Table 6. Recommendations for Dose Modification of Study Drug(s) Based on Type and Severity of Adverse Event or Laboratory Abnormality

Non-Hepatic and Non-Hematological Study Drug-Related Event				
CTCAE Grade	Grade 1	Grade 2	Grade 3	Grade 4
Idelalisib and Ofa Dosing Recommendation	Maintain dose level	Maintain dose level	Withhold drugs until toxicity is Grade ≤1. May resume idelalisib only at next lower dose level for most toxicities, but may resume at current dose level in the case of grade 3 infections, grade 3 nausea/vomiting/diarrhea that can be symptomatically managed, grade 3 asymptomatic laboratory abnormalities or grade 3 infusion reactions.	
Hepatic Study Drug-Related Event (Elevation in ALT, AST, or Bilirubin)				
CTCAE Grade	Grade 1	Grade 2	Grade 3	Grade 4
ALT/AST	>ULN-3 x ULN	>3-5 x ULN	>5-20 ULN	>20 x ULN
Bilirubin	>ULN-1.5 x ULN	>1.5-3 x ULN	>3-10 x ULN	>10 x ULN
Idelalisib and Ofa Dosing Recommendation	See Section 6.2: Management of Hepatic Events.			
Hematological Idelalisib -Related Event				
IWCLL Grade	Grade 1	Grade 2	Grade 3	Grade 4
Neutropenia (ANC x 10 ⁹ /μL)	ANC <LLN-1.5	ANC <1.5-1.0	ANC <1.0-0.5	ANC <0.5
Thrombocytopenia (platelets x 10 ⁹ /μL)	Platelets 11-24% below baseline	Platelets 25-49% below baseline	Platelets 50-74% below baseline	Platelets ≥75% below baseline or ≤25K
Idelalisib Dosing Recommendation	Maintain dose level	Maintain dose level	Maintain dose level; support with g-CSF growth factors at investigator discretion	During combination therapy period, consider G-CSF support and maintain current study drug dose level and schedule. During initial and continuing single-agent study drug therapy period, consider G-CSF support and continue study drug at initial or lower dose level at investigator discretion.

***Note: In any case where Idelalisib is held, ofatumumab should also be held. The assessment schedule is also held in cases where study drug is held for greater than half a week.*

Abbreviations: ALP, alkalkine phosphatase; ALT, alanine aminotransferase; ANC, absolute neutrophil count; AST, aspartate aminotransferase; CTCAE, Common Terminology Criteria for Adverse Events; LLN, lower limit of normal; ULN, upper limit of normal

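### The rule that pauses the assessment schedule during a drug hold was not reconciled with the idelalisib stop, and exempts neither progression checks nor routine safety visits

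*Combined protocol and SAP*

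**What the plan says.** **Holds.** Section 6.1 links the two drugs: "Please note that if one study drug is held, the other will also be held". It then links the visit calendar to dosing: "If drugs are held for more than half a week, then the assessment schedule will also be held until drug resumption". The note under Table 6 repeats the first rule as "In any case where Idelalisib is held, ofatumumab should also be held" and also pauses the assessment schedule for holds of more than half a week, without saying when the pause ends. Section 6.2 sets the length allowed: "Either or both drugs may be held for up to six weeks for resolution of toxicity without removing a participant from the study". After induction, longer holds are allowed once discussed with the overall principal investigator.

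**Amendment of 3/14/16.** Section 5 states "All therapy with idelalisib has been discontinued. Patients on drug stopped as of 3/11/16", and Section 5.2.1 states "Idelalisib will not be given". Ofatumumab goes on: "Those currently receiving ofatumumab may complete the planned course and evaluations as below". On follow-up of these patients, Section 2.5 states "They will undergo a full disease restaging with correlative samples within 30 days and be followed per protocol until further therapy".

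**Endpoint.** Section 10.1.7 counts PFS from study entry. Section 14.2 estimates its median by Kaplan-Meier and does not mention assessments moved by a hold.

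**The concern.** There are two separate problems.

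1. The hold rules were written for two drugs that can each be interrupted and restarted. They remain in force now that one drug is permanently stopped and the other continues. Sites need to know whether the stop triggers the joint hold and the pause.

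2. Whatever the answer to the first, the pause covers the schedule as a whole. A patient held for toxicity is seen later for scheduled progression checks and routine safety visits, while the PFS clock keeps running. Timing of ascertainment then depends on toxicity. Holds were foreseeable: Section 2.5 reports grade 4 transaminase elevation in two of the first eight patients to reach cycle 2, and Section 6.2 generally holds idelalisib from grade 2 upward at a first event, with a discretionary exception for stable low-grade elevations.

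**Working it through.** The plan states no figure for this point, so none can be reproduced. The check is a comparison of passages followed by calendar arithmetic.

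**Step 1: does the idelalisib stop count as a hold?**
- Sections 5 and 5.2.1 describe the stop as discontinuation. Section 6.2 uses hold for a toxicity interruption, limited to six weeks in induction. The usual sense is therefore that discontinuation is not a hold.
- No passage says so. Section 6.1 and the Table 6 note were not adapted to ofatumumab given alone.
- One case stays open on either reading: a patient whose idelalisib was already held for toxicity on 3/11/16. That patient was held under Section 6.1, and idelalisib cannot resume. Section 2.5 gives a restaging within 30 days, but nothing says when the regular calendar restarts.

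**Step 2: what is exempt from the pause?**
- *Continues under its own rule:* liver tests (Section 6.2), hepatitis B DNA at least every 2 months in core-antibody-positive patients (Section 6.2; Table 10, footnote 10), PML work-up and follow-up (Section 6.2), adverse-event collection (Section 6) and follow-up to resolution (Section 11.8).
- *No exemption found:* scheduled physical examination, hematology and the adverse-event review that Table 10 ties to the examination. Section 10.1.3 notes that nodal progression is often found on examination, so these visits are also progression checks.

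**Step 3: how far can visits move?** Inputs are 28-day cycles, with cycle 4 lasting 49 days (Section 5), and a hold of up to 6 weeks = 42 days (Section 6.2).
- Cycle 3 day 1 = 57; cycle 4 day 1 = 57 + 28 = 85; cycle 4 day 22 = 85 + 21 = 106.
- Cycle 5 day 1 = 85 + 49 = 134; cycle 8 day 1 = 134 + 3 × 28 = 218; cycle 10 day 1 = 134 + 5 × 28 = 274.
- Monthly examinations in cycles 5-8: 4 weeks apart; with one maximal hold, 4 + 6 = 10 weeks.
- The shortest hold that triggers the pause is just over 3.5 days, so the delay per induction hold runs from about 0.5 to 6 weeks. Post-induction there is no stated limit.

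**Step 4: what this does to a progression date.** Assume that progression starts at a uniformly distributed time between two visits and is found only at the next one. The mean lag is half the interval: 4/2 = 2 weeks without a hold, 10/2 = 5 weeks in the stretched interval. This is an illustration for one patient and one interval. Once the regular spacing returns, the lag returns to its usual size.

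**Step 5: intervals that do not measure the problem.** The gap between the CT scans at cycle 4 day 22 and cycle 10 day 1 is 274 − 106 = 168 days, and 168 + 42 = 210 days with a maximal hold. These restagings are tied to drug exposure and may properly move, so this is not counted as harm.

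**The case against.** **The stop is a discontinuation, not a hold.** This is the better reading. A reader might infer that since 3/11/16 the pause has no end and ofatumumab must stop. The documents do not support that: Sections 1.1, 2.5, 5 and 5.4 let ofatumumab or follow-up continue, and the resumption in Section 6.1 is not limited to idelalisib, so restarting held ofatumumab can satisfy it. What stands is leftover text, an undefined term and the patient already on hold.

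**Safety is watched during a hold.** A reader might infer that safety monitoring as a whole is suspended, or that only hepatic events are covered. Neither is right, given the rules listed in Step 2. Table 6 also withholds drugs until non-hepatic, non-hematological toxicity falls to grade 1 or less, which requires reassessment. What stands is narrower: routine examination, hematology and adverse-event review can slip. Pneumonitis and colitis, both named in the protocol as observed toxicities, have no separate visit schedule during a hold.

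**Tying assessments to exposure is sensible.** It is, for the restagings at cycle 2 day 22 (idelalisib alone) and cycle 4 day 22 (last weekly ofatumumab dose) and for the final restaging two months after ofatumumab. A shift of the final restaging from day 274 to day 274 + 42 = 316 is therefore no evidence of harm. The argument does not extend to a time-to-event endpoint counted from study entry.

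**Little is left to change.** Enrollment closed at 27 and idelalisib is stopped, so new wording cannot alter past holds. It can still govern ofatumumab holds, and an analysis rule can still deal with shifts that have already happened.

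**Conclusion.** The point holds in a limited form. Section 6.1 and the Table 6 note are current text that was not reconciled with the amendment, and the status of the permanent stop is undefined. Independently of the amendment, the pause can delay progression checks and routine safety visits by up to 6 weeks per induction hold, and only in patients whose drugs were held.

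The 6-week figure assumes one hold of the maximum length with the pause applied as written. A patient's recorded progression is later only if it arises in the stretched interval and is not picked up at an unscheduled visit. The documents do not give the number of patients held or the dates, so a reader who infers that median PFS is biased by a known amount goes further than they allow. PFS here is a descriptive, single-arm secondary endpoint, and Section 10.1.3 leaves imaging for progression to the physician. This deserves correction but does not touch the primary response-rate design.

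**What to change.** 1. Reconcile Section 6.1 and the Table 6 note with Sections 2.5, 5 and 5.2.1. State whether permanent discontinuation of idelalisib is a hold, and how the calendar runs for a patient who was on a toxicity hold on 3/11/16. Which answer is right is for the sponsor; the passages must agree.

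2. State that progression checks and routine safety assessments already in Table 10 continue on calendar time from cycle 1 day 1 during any hold. The exposure-linked restagings (cycle 2 day 22, cycle 4 day 22, final) and the pharmacokinetic draws may move with dosing.

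3. Add to Section 14.2 that PFS uses actual assessment dates, with a sensitivity analysis for patients whose assessments were shifted by a hold. One form re-dates a progression found at a delayed visit to that visit's unshifted date, but never before the last progression-free assessment. Report the number of patients affected and the length of each shift.

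The cost is protocol wording, one small additional analysis and the retrieval of hold dates. The visits are already planned. The downside is that some will fall during a hold. No dose or hold rule is proposed.
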